¹³Blood pressure and heart rate are also assessed at the start of every session for patients in the SE (intervention) arm who are known to have high blood pressure, history of unstable blood pressure, symptomatic, or reports new treatment. If 2/3 readings demonstrate the pressure to be >160 OR >90 at the time of the session, exercise will be held on that day.

¹⁴Continuously reported from informed consent until 28 days after Cycle 24, Day 1. All adverse events (AE) should be followed to their resolution, until the PIs assess them as stable, irreversible, or until the patient refuses further follow up, whichever comes first. AEs are assessed by the exercise physiologist, trainer, etc. at on-site exercise visits and in all subjects (in person or by phone) on a monthly basis. AE events will be recorded on the AE form and logged in REDCap. AE assessment will include bone pain.

¹⁵Medications will be reviewed with the patient once a month, either in person or by phone call. Medications will be logged and entered into the REDCap database.

¹⁶Sec 8.3: Baseline blood collection will occur after the patient passes the baseline CPET, and will occur before or on Day 1, Cycle 0, before the remainder of the exercise tests are performed and at least 48 hours after any vigorous activity including the screening CPET visit

¹⁷Sec 8.3: Follow-up blood collection will occur prior to completing the exercise tests on that day (see footnote #11), and at least 48 hours after any vigorous activity. If it cannot be completed on that day, it must be completed within 7 days after Day 1 of the Cycle, at least 48 hours after any vigorous activity.

¹⁸Request access to available archival formalin-fixed paraffin-embedded (FFPE) tumour blocks or tumour slides from consenting patients for future biomarker analyses.

¹⁹The baseline surveys or FFQ will be completed within 28 days prior to the screening CPET and used as the baseline assessments

²⁰[Appendix 6, 20-27, 29, 31, 33](#). All follow-up surveys and FFQ will be completed within 7 days before the exercise assessment, except for [Appendix 20, 24, and 33](#), which are completed on paper at the visit or by mail.

²¹Selected assessments will be administered during the follow-up period on a yearly basis. If no response is received from the participant and medical records do not indicate death, we will follow up with the next of kin or alternate contact.

⁸New conditions diagnosed on-study are recorded during the on-study period.

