5.5.4.1 Record date of assessment

5.5.4.2 Confirm completion of questionnaires

5.5.4.3 Record any adverse events and changes to concomitant medications. Record bone pain (VAS) and fatigue (VAS).

5.5.4.4 Record resting measures including resting blood pressure, resting heart rate and SpO₂, ECOG

5.5.4.5 Perform cardiopulmonary exercise test with ECG (Day 1 of cycle 6 and 12 only)

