5.5.4.6 Perform 400m walk test (Day 2)

5.5.4.7 Perform 1RM strength assessment chest press, leg press, seated row, and leg extension (Day 2)

5.5.4.8 Complete Constant Load Exercise Test (Day 2).

NOTE: Please see [Table 1](#), footnote 14 for adverse events collection & reporting, and [Table 1](#), footnote 15 for medication collection & reporting.

5.5.5. Cycle 0 (within 7 days on or after Day 1) – One to three Exercise Training Visits per 7 days for ARM A

Exercise session (1 to 3 supervised exercise sessions per 7 days – refer to Section 6.1 for details)

▪ **Day 1**

- **Assessment:** Bone pain (VAS), Fatigue (VAS), resting heart rate, resting blood pressure, and record any new adverse events or changes to medication.
- **Warm up:** 5 minutes cycling at a light to moderate intensity
- **Exercise:** High load, low volume resistance training; high-intensity interval aerobic training.
- **Outcomes:**
 - Resistance Exercise: Number of sets, number of repetitions, weight lifted.
 - Aerobic Exercise: Work interval, rest interval, number of repetitions, RPE achieved.
 - Sessional Data: Sessional RPE, post-aerobic heart rate, post-session blood pressure

- **Cool down:** Trunk flexion and extension exercises and static stretching
 - **Day 2**
 - **Assessment:** Bone pain (VAS), Fatigue (VAS), resting heart rate, resting blood pressure and record any new adverse events or changes to medication.
 - **Warm up:** 5 minutes cycling at a light to moderate intensity
 - **Exercise:** High intensity continuous aerobic training
 - **Outcomes:**
 - Aerobic Exercise: Work interval, rest interval, number of repetitions, RPE achieved.
 - Sessional Data: Sessional RPE, post-aerobic heart rate, post-session blood pressure
 - **Cool down:** Trunk flexion and extension exercises and static stretching
 - **Day 3**
 - **Assessment:** Bone pain (VAS), Fatigue (VAS), resting heart rate, resting blood pressure and record any new adverse events or changes to medication.
 - **Warm up:** 5 minutes cycling at a light to moderate intensity
 - **Exercise:** Moderate load and volume resistance training; high-intensity interval aerobic training
 - **Outcomes:**
 - Resistance Exercise: Number of sets, number of repetitions, weight lifted.
 - Aerobic Exercise: Work interval, rest interval, number of repetitions, RPE achieved.
 - Sessional Data: Sessional RPE, post-aerobic heart rate, post-session blood pressure
 - **Cool down:** Trunk flexion and extension exercises and static stretching

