6.1 Supervised Exercise Plan (Cycles 0-11)

The exercise intervention will include 48 weeks of aerobic and resistance training three times per week with the goal of delivering three moderate-to-vigorous aerobic training sessions and two structured resistance training sessions each week. A total of 88 supervised sessions should be completed within Year 1, in the event that the patient does not have any AEs that would prohibit him from reducing the number of exercise sessions. As long as the prescribed supervised dose is 88 sessions in Year 1, there is flexibility regarding the number of supervised sessions in a given week in Year 1.

Original Program: We strongly advise patients to adhere to the original program, with patients receiving three supervised exercise sessions in weeks 1-4 (Cycle 0), prior to the supervised exercise sessions tapering

throughout the program to two supervised sessions and one self-managed session for weeks 5-36 (Cycles 1-8) and one supervised training session and two self-managed sessions for weeks 37-48 (Cycles 9-11).

Flexible Entry: Although patients randomised to Supervised Exercise are **requested** to complete 3 supervised exercise sessions per week during Cycle 0 (totalling 12 supervised exercise sessions in this cycle), we recognise that some patients may require an 'easier' entry into the study in order to agree to enrol. This **flexible entry** option is permitted, where patients may complete a minimum of 1 to a maximum of 3 supervised sessions each week in Cycle 0, prior to joining the 'full program' from Cycle 1 onwards. However, while we allow the flexibility of less than 3 supervised sessions per week, those sessions will need to be made up later in Year 1 such that they complete the 88 sessions within Year 1. If using a flexible entry option, please prioritise the combined high-intensity interval training and resistance training sessions (Day 1 or Day 3 above) as it is easier to insert moderate-intensity continuous training sessions (Day 2) later in the program, when recovering missed supervised sessions. Examples of flexible entry plans are included in the SOM.

Exercise prescription will be tailored to the participant's baseline cardiopulmonary and strength assessments, and baseline conditions. The three training sessions each week will be **generally** structured as follows, with subtle alterations for variety, periodisation **and autoregulation**:

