6.1.8 Behavioural Support Program (Intervention Arm Only)

Participants will be asked to complete at least one unsupervised exercise session per week (hereafter referred to as self-managed exercise) starting in Week 5 (Cycle 1). The more self-managed exercise the participants are asked to engage in, the more behavioural support will be provided. The behavioural support will be provided utilizing text messages rooted in constructs/strategies from Social Cognitive Theory (SCT) and the Theory of Planned Behaviour (TPB). The overarching focus of the behavioural support will be to increase/enhance perceived control in task-specific exercises and overcoming individual barriers to exercise. The behavioural support provided will be encompassing, consistently delivered, and provided to each participant throughout the program. There will be four 'levels' of behavioural support ([Table 4](#)):

1. [3x/week supervised \(cycle 0\)](#)

2. 1x/week self-managed; 2x/week supervised (cycles 1-8)
3. 2x/week self-managed; 1x/week supervised (cycles 9-11)
4. Totally self-managed; 1x/cycle supervised (cycles ≥ 12)

Table 4. Guidelines for Level of Behavioural Support

Level of Self-Management	Behavioural Support Components
No self-management 3x week supervised Cycles 0	The behavioural support will focus on: 
 ○ Perceived competence ○ Identifying and overcoming barriers to exercise ○ Goal setting ○ Enhancing self-efficacy 
 ➤ 1x per week pt. would get a text message/e-mail emphasising one of the topics above “signed” by the exercise specialist. Each week would be a different message working “down” off the list
1x week self-managed; 2x week supervised Cycles 1-8	The behavioural support will focus on: 
 ○ Perceived independence ○ Securing social support ○ Maintaining/enhancing self-efficacy ○ Identifying and overcoming barriers to exercise ○ Self-monitoring ○ Goal setting 
 ➤ 2x per week pt. would get a text message emphasising 2 of the topics above “signed” by the exercise specialist – each week would be a different pair working “down” off the list.

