13.1 Definitions

13.1.1 Clinical Adverse Events (AE)

A clinical adverse event is any unfavourable or unintended sign, symptom, or disease temporally associated with the study intervention and occurring in a patient assigned to the intervention. All AEs reported from the date of informed consent until 28 days after the Off-Study visit will be considered. AEs are assessed by the exercise physiologist, trainer, etc. at on-site exercise visits and in all subjects (in person or by phone) on a monthly basis. This includes adverse clinical or laboratory findings, illness, or an exacerbation or progression of a disease/condition present at baseline. A list of standard questions will be used to assess any AEs, provided in the SOM.

In this trial, the study intervention is defined as supervised aerobic and resistance exercise. All potential participants will be screened via their medical charts as well as through in-person assessments to assess cardiovascular contraindications to exercise. Our multi-gated comprehensive approach should systematically identify and screen out any individual for whom this study is contraindicated.

However, rare but serious AEs are possible. Those that may occur during either cardiopulmonary exercise testing (CPET) or exercise training include myocardial infarction (heart attack), stroke, unconsciousness or other serious injury.

- Events during a CPET are rare (<1/100,000 in well individuals and 1/10,000 in sick individuals). A trained health professional (e.g. medical staff and exercise physiologist) will monitor the exercise test in a location staffed by physicians, in the rare event that such an event occurs.
- Similar to a CPET, exercise training may cause temporary risks of an adverse cardiovascular event, such as a heart attack. The CPET with ECG-monitoring that must be completed prior to randomisation will ensure that all randomised participants are healthy enough to engage in exercise training.

Absolute and relative indications for stopping exercise (both testing and training) are provided in [Table 5](#). In the event of a participant presenting with any of the below symptoms exercise should be stopped.

Table 5. Indicators for Stopping Exercise

Absolute indications for Stopping Exercise:

- Suspicion of a myocardial infarction or acute myocardial infarction (heart attack)
- Onset of moderate-to-severe angina (chest pain)

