13.7 Statistical Analysis of Adverse Events

Adverse event rates will be summarised with frequency and percentage within each arm and across arms. Rates between groups will be compared using the intention-to-treat approach. In addition, AE incidence rates will be summarised by severity and relationship to the intervention. Intervention-related AEs are those judged by the Investigator to be at least possibly related to the intervention. Adverse events with missing severity or relationship to the intervention will be classified as severe and treatment-related, respectively. Patients with multiple occurrences of events will only be counted once at the maximum severity for each preferred term, SOC, and overall. Deaths that occur within 28 days after the 24th cycle clinic visit are defined as on-study deaths.

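### The adverse-event definition, as worded, leaves out control men and contradicts two-arm collection; more frequent asking in the exercise arm also puts the comparison of non-serious events at risk of detection bias

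*Combined protocol and SAP*

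**What the plan says.** **Definition.** Section 13.1.1 of the protocol describes a clinical adverse event as something "temporally associated with the study intervention and occurring in a patient assigned to the intervention". It adds that "the study intervention is defined as supervised aerobic and resistance exercise". Section 13.1.2 builds the serious adverse event (SAE) on the same base term.

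**Collection.** The same subsection counts events from informed consent, and it and Table 1 footnote 14 have them assessed "at on-site exercise visits and in all subjects (in person or by phone) on a monthly basis", with a standard question list. The exercise assessment visits at Cycles 6, 12, 18 and 24, held in both arms, carry the instruction "Record any adverse events and changes to concomitant medications" (Section 5.5.4). The Cycle 24 visit and the safety follow-up (5.5.10, 5.5.11) also cover both arms. For Arm A only, the session templates in Sections 5.5.5 to 5.5.7 tell staff to "record any new adverse events or changes to medication" at each training session. On the number of sessions: "A total of 88 supervised sessions should be completed within Year 1" (Section 6.1), and from Cycle 12 the pattern is "Totally self-managed; 1x/cycle supervised" (Section 6.1.8).

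**Analysis.** Section 13.7 summarises events within each arm and states: "Rates between groups will be compared using the intention-to-treat approach". A man with repeated events counts once per preferred term, at maximum severity. No test is named, and nothing is said about how often each arm is asked. Section 4.6 states that patients and staff are not blinded.

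**The concern.** There are two separate problems.

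The first is wording. If an event must occur in a man assigned to supervised exercise, then control men have no adverse events, and neither does anyone between consent and randomisation. Because the SAE definition rests on the same term, it inherits the fault. A site that applied the definition rather than the visit schedule would under-report controls, and the between-arm comparison would lose its reference rate.

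The second is ascertainment. Men seen two or three times a week and asked each time will mention aches, minor falls and brief symptoms that a man asked once a month may have forgotten. Exercise-arm sessions also include a bone-pain score and resting blood pressure, and Section 13.1.1 allows abnormal test findings to count as events. With both arms unblinded, an excess of minor events in Arm A could come from exercise, from asking, or from both. Section 13.7 gives no means of separating these, and the list of recorded event details in Section 13.0 does not include where the report came from. The monitoring committee reviews safety quarterly once 50 men are enrolled (Section 15.7), so distorted counts could influence decisions while the trial is running.

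**Working it through.** **1. The definition against the rest of the plan.**
- Section 13.1.1, definition: men assigned to supervised exercise only.
- Section 13.1.1, window: from consent, which precedes assignment.
- Section 13.1.1 and Table 1 footnote 14: monthly in every man.
- Sections 5.5.4, 5.5.10, 5.5.11: both arms.
- Section 13.7: summarised within each arm and compared.

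The definition cannot be satisfied together with the other four. They agree with one another, so two-arm collection is the evident intention and the definition is the sentence that is wrong.

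**2. The plan's figure of 88 sessions.** Section 6.1 gives 3 a week for 4 weeks, 2 a week for 32 weeks and 1 a week for 12 weeks: 12 + 64 + 12 = 88. It reproduces exactly.

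**3. Scheduled asking occasions.**
- Year 1: 88 supervised sessions against 12 monthly control contacts, 88/12 = 7.3.
- Cycles 1 to 24: Arm A has 88 + 12 (one supervised session per cycle from Cycle 12) = 100; controls have 24 monthly contacts; 100/24 = 4.2.
- Adding the assessment days both arms share (two each at Cycles 6 and 12, one each at Cycles 18 and 24, so 2 + 2 + 1 + 1 = 6): 106/30 = 3.5.

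The 100 includes the Cycle 0 sessions. These counts assume that Arm A's monthly contact coincides with a session, which footnote 14 permits. If it were always separate, the last two ratios would be (100 + 24)/24 = 5.2 and (106 + 24)/30 = 4.3. Self-managed sessions, which carry the same event line in Sections 5.5.6 and 5.5.7, are not counted.

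**4. What such an imbalance could do (illustration only).** The documents give no event rates or capture probabilities, so every input here except the sample size is assumed. Take 866/2 = 433 men per arm, the same true incidence p in both arms, a two-sided 5% comparison of proportions, and capture of 95% in Arm A against 85%, 75% or 65% in controls. The observed proportions are p1 = 0.95p and p2 = capture × p, and the apparent risk ratio is 0.95/capture. The chance of a significant excess in Arm A is Φ[((p1 − p2) − 1.96·s0)/s1], where s0 is the pooled and s1 the unpooled standard error.

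| Control capture | Apparent risk ratio | Chance, p = 10% | Chance, p = 30% |
|---|---|---|---|
| 85% | 1.12 | 7% | 17% |
| 75% | 1.27 | 18% | 53% |
| 65% | 1.46 | 37% | 87% |

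Example (75%, p = 30%): p1 = 0.285, p2 = 0.225, s0 = 0.0296, s1 = 0.0296; (0.060 − 0.0581)/0.0296 ≈ 0.07, giving 53%. With equal capture, the chance in this direction would be 5%/2 = 2.5%.

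**The case against.** The strongest reply is that the plan works despite the sentence. A reader might infer from the definition that control events are not collected at all. The documents do not support that: several sections require two-arm collection, and a site following the schedule would not omit controls. This stands, and it makes the definition a contradiction to reconcile rather than an exclusion in operation.

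A reader might also infer that the whole safety comparison is biased by design, or that the trial cannot tell whether exercise raises falls, pain or cardiac events. That goes too far. The monthly contacts cover the same calendar time in both arms with standard questions, and each man counts once per preferred term, so extra asking matters only where monthly recall misses an event. That is plausible for mild or transient events and much less so for SAEs and deaths. Falls are collected by questionnaire every three cycles. Pain is measured by questionnaire at Cycles 6, 12, 18 and 24 and compared under Section 12.7. Skeletal events draw partly on medical records (Section 11.2). An infarction or stroke would ordinarily meet an SAE criterion.

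Finally, the ratio of asking occasions is not a measure of bias, and the Year 1 ratio of 7.3 overstates the imbalance for the full intervention period. This also stands.

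What the reply does not meet is that Section 13.7 compares all events between unblinded arms with no allowance for the unequal schedule.

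**Conclusion.** Two narrow points hold. The definition in Section 13.1.1 is wrong as worded and must be brought into line with two-arm collection from consent and with Section 13.7. The comparison of non-serious, mild or transient events is at risk of detection bias toward more events in Arm A, because scheduled asking there is about 3.5 to 4.2 times that in controls over Cycles 1 to 24, assuming Arm A's monthly contact falls within a session.

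The direction follows from the schedule. The size does not: the risk ratios of 1.12 to 1.46 in the illustration rest on assumed capture rates and show only that modest differences in capture could produce a false signal. SAEs, deaths and the questionnaire measures are much less exposed, and the primary endpoint is not affected.

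**What to change.** 1. **Section 13.1.1:** define an adverse event as any untoward event in any consented or randomised man in either arm, whether or not related to the intervention. Section 13.3 already handles attribution.
2. **AE form:** record the source of each report (training session, monthly contact, shared assessment visit, medical record), unless the form in the operations manual, which is not in the documents, already does so.
3. **Monthly contact:** ask the full standard list in both arms, covering everything since the previous monthly contact, including events already logged at a session. Without that last clause, Arm A events noted at sessions could drop out of the comparison while control events stayed in, which could hide real harm.
4. **Section 13.7:** base the between-arm comparison of non-serious events on the monthly contacts and shared assessment visits. Add all SAEs, deaths and grade 3 or higher events from any source.
5. **Reporting:** show the all-source comparison alongside, and list Arm A events found only at sessions separately.

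The cost is a reworded definition, at most one extra field, slightly more work at the monthly contact and one more table. Some minor Arm A events will sit outside the main comparison, though they remain visible. The change reduces the asymmetry but does not remove it: session prompts may still help Arm A men recall events at the monthly contact, and the trial remains open label.

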5.0 CLINICAL PROCEDURES

Guidelines for Pre-Study Testing:

All laboratory tests that are specified in the eligibility criteria (absolute neutrophil count, platelet count, creatinine, bilirubin, aspartate aminotransferase, PSA, serum testosterone) as well as blood-based markers that are part of the Halabi score should be completed within 28 days before Cycle 0, Day 1 (see footnote #7). The CPET must be completed within 14 days of Cycle 0, Day 1. Participants are randomised after the CPET.

Table 1. Summary of assessments. One cycle = 28 days. (Next page)

Table 1 Summary of Assessments	Screening	On-Treatment Study Period ¹																								Off-Treatment		
		Cycle 0: Baseline ²	Supervised Exercise								Transition			Self-managed exercise program														Follow-up Period
		0	1	2	3	4	5	6	7	8	9	10	11	12	13	14	15	16	17	18	19	20	21	22	23	24		
Informed Consent	X																											
Randomisation	X ⁴																											
Clinical History																												
Medical history ^{&}	X																										X	
Tumour histology	X																											
Medication/Tx history	X				X			X			X			X			X			X			X			X		
Body Measurements																												
Height	X ³																											
Weight, waist, hip circumference	X ³							X ⁵						X ⁵					X ⁵							X ⁵		
Lab Studies																												
CBC w/diff, blood chemistries ⁶	X ⁷				X ⁶			X						X ^{6,8}			X ⁶			X ^{6,8}			X ⁶			X ^{6,8}		
Fasting Lipid Profile (LDL, HDL, Triglycerides), fasting Glucose, HbA1c		X						X																				
Efficacy																												
Overall survival status, Disease progression, Symptomatic-skeletal event ⁹								X ⁹						X ⁹					X ⁹						X ⁹		Twice yearly ⁹	
WHO analgesic scale	X				X			X			X			X			X			X			X			X	Once yearly ⁹	
CPET with ECG ³	X ¹⁰							X ¹¹						X ¹¹														
ARM A - Constant Load test ¹⁰		X ¹⁰	X	X	X	X	X	X	X	X	X	X	X	X	X	X	X	X	X	X	X	X	X	X	X	X	X	
ARM A - 1-RM Strength test		X ¹⁰						X ¹¹			X ¹¹			X ¹¹					X ¹¹						X ¹¹			
ARM B - 1-RM Strength test		X ¹⁰						X ¹¹						X ¹¹					X ¹¹						X ¹¹			
400 m walk test		X ¹⁰						X ¹¹						X ¹¹					X ¹¹						X ¹¹			
Safety																												
Medical Clearance(s) ¹²	X							X						X					X									
Vital signs ¹³	X ³	X						X						X					X							X		
ECOG performance status	X				X			X			X			X			X			X			X			X		
Bone pain at exercise visits			Assessed at each supervised exercise visit using VAS																									

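### The adverse-event comparison sets no start at randomisation, so events from consent onward enter both arms and slightly dilute the any-grade contrast

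*Combined protocol and SAP*

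**What the plan says.** Section 13.1.1 gives the window: "All AEs reported from the date of informed consent until 28 days after the Off-Study visit will be considered". The synopsis, Table 1 footnote 14 and section 13.5.3 also start collection at consent.

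Section 13.7 gives the analysis. On the comparison: "Rates between groups will be compared using the intention-to-treat approach". On counting: "Patients with multiple occurrences of events will only be counted once at the maximum severity for each preferred term, SOC, and overall". It adds a second summary, "In addition, AE incidence rates will be summarised by severity and relationship to the intervention", and a rule for gaps: "Adverse events with missing severity or relationship to the intervention will be classified as severe and treatment-related, respectively". It gives no onset rule, and no section defines a treatment-emergent set.

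On sequence, section 5.0 says "Participants are randomised after the CPET" and "The CPET must be completed within 14 days of Cycle 0, Day 1". Section 5.5.1.8.1 has adverse events since consent reviewed at the screening CPET visit, so events from before randomisation will be in the database.

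**The concern.** Intention-to-treat settles who is analysed and in which arm. It does not settle when events begin to count. An event before randomisation cannot be caused by the allocation and is equally frequent in both arms in expectation. Including it adds the same background to each arm and moves the comparison towards no difference, which is the wrong direction of error for a safety analysis.

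Once-per-term counting adds to this. A man with muscle soreness in screening is already counted for that term, so a later episode of the same or lower grade changes nothing. Screening includes a test to exhaustion, and Table 1 footnote 10 lets the one-repetition-maximum tests be done on the CPET day. Events provoked by such tests could plausibly be the soreness, joint pain and strains that section 13.2 lists as expected.

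**Working it through.** **No plan figure to reproduce.** The documents state no adverse-event rate, margin or power. All rates below are assumptions.

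**Inputs from the documents**
- Screening: up to 28 days before the CPET (5.5.1), then up to 14 days to Cycle 0 Day 1 (5.0). 28 + 14 = 42 days. This is an upper bound, because randomisation comes before Cycle 0 Day 1 (Table 1 footnote 2).
- On study: 24 cycles × 28 days + 28 days = 700 days.
- Screening share of the window: 42 / 742 = 5.7% at most.
- Men per arm: 866 / 2 = 433.

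**Dilution.** Let s be the share of men with the term before randomisation, and p the true risk afterwards. If the two are independent,

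observed risk = 1 − (1 − s)(1 − p),

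so the risk difference shrinks by the factor (1 − s).

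**s at a constant background rate.** With an assumed control risk of 20% over 700 days, s = 1 − 0.8^(42/700) = 1.3%.

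**Assumed true risks of 40% (exercise) and 20% (control)**

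| s | Exercise | Control | Risk difference | Risk ratio |
|---|---|---|---|---|
| 0 | 40.0% | 20.0% | 20.0 points | 2.00 |
| 1.3% (constant rate) | 40.8% | 21.1% | 19.7 points | 1.94 |
| 5% (assumed) | 43% | 24% | 19 points | 1.79 |
| 10% (assumed) | 46% | 28% | 18 points | 1.64 |
| 20% (assumed) | 52% | 36% | 16 points | 1.44 |

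**Effect on detection.** With 433 men per arm, two-sided 0.05, and assumed risks of 29% and 20%, power is 87% when only post-randomisation events count. It is 85% at s = 1.3%, 80% at 5%, 72% at 10% and 58% at 20%. A less common term is more sensitive: for 6% against 2%, the ratio of 3.0 becomes 2.9 at the constant-rate s of about 0.1%, but 1.55 at s = 5%.

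**How often a repeat event is hidden.** Suppose the earlier and later grades have the same distribution and are independent. With grades 1/2/3 at 70/25/5%, the later event is no worse than the earlier with probability 0.70 × 0.70 + 0.25 × 0.95 + 0.05 × 1 = 0.78. With 50/30/20% it is 0.50 × 0.50 + 0.30 × 0.80 + 0.20 × 1 = 0.69. The remaining 22% to 31% appear at the higher grade, although the any-grade count does not change. This applies only to men who had the term in screening.

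**The case against.** **The plan does not say that the comparison starts at consent.** A reader might infer that it does, but section 13.7 gives no window and the sentence in 13.1.1 stands under definitions. This is fair. The defect is a silent 13.7 beside a single stated window, and a programmer following the text would use that window.

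**Section 13.1.1 also defines an adverse event more narrowly.** It ties the event to the study intervention and to a patient assigned to it, and the intervention is supervised exercise. That would drop screening events. Read literally, it would also drop every control-arm event, which contradicts the comparison in 13.7 and the monthly review of all subjects in Table 1 footnote 14. It does not rescue the plan; it is a second point to reconcile.

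**Exercise-related events are not hidden in general.** A reader might infer that they are. The documents do not support this: the worst grade is kept, and incidence is also summarised by relationship. Two limits remain. Attribution is made by unblinded investigators (4.6, 13.3), so that summary cannot replace the randomised comparison. And 13.7 does not say whether once-per-term selection is made before or within the relationship split.

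**Bone pain is partly protected.** Grade 2-3 bone pain is excluded at entry (3.2), so bone pain carried into the trial should be mild, and later grade 2 or worse would show.

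**Other routes exist.** Symptomatic fracture is compared as a skeletal event timed from randomisation (11.2, 12.6), pain by questionnaire (12.7), and falls are collected by questionnaire in both arms. The safety committee reviews specific cases quarterly (13.6). What is left is mainly lower-grade soreness, joint pain and strain.

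**The larger figures have no source.** This is correct: nothing in the documents supports 5% to 20%. They show what would have to be true for the effect to matter.

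**Conclusion.** The gap is real and its expected size is small. As written, the any-grade comparison includes pre-randomisation events in both arms and is diluted towards no difference. At a constant background rate, with an assumed 20% control risk and the longest screening period, about 1.3% of men are affected and an assumed risk ratio of 2.0 becomes about 1.94. Only a term that is common at entry or provoked by testing before randomisation would be materially affected (1.79 to 1.44 at an assumed 5% to 20%). These figures take pre- and post-randomisation events as independent. The documents do not support a claim of substantial or general masking of exercise harm, and with no adverse-event hypothesis or margin specified, no stated conclusion is overturned. This is a free improvement, minor in expected size.

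**What to change.** Keep collection from consent unchanged. In section 13.7:
- restrict the between-arm comparison to events with onset, or worsening in grade, on or after randomisation;
- apply once-per-term counting within that set, and within each level of the relationship split;
- tabulate events from consent to randomisation separately, pooled over arms;
- do not classify a missing relationship as treatment-related when onset was before randomisation.

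In section 13.1.1, reconcile the definition that ties an event to a patient assigned to the intervention with the consent-based window and the two-arm comparison.

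The cost is a few sentences and a date filter. Section 13.0 already has timing recorded on the case report form, so no new data are needed. The filter removes only what precedes randomisation. Events provoked by strength testing on Cycle 0 Day 1 stay in the comparison for both arms.
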